4.4 Replacement of subjects

Replacement of Patients in Run in Phase

Patients who received <90% of the durvalumab and tremelimumab infusion in Cycle 1 (e.g., because the infusion had to be discontinued due to an infusion reaction) and did not experience a DLT will not be taken into account in the assessment of the overall DLT rate for the phase I run in cohort and need to be replaced.

If a patient experiences a DLT in Cycle 1, study therapy may be discontinued following discussion and agreement between the Sponsor and Investigator.

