Both durvalumab and tremelimumab have well established toxicity profiles as a single agent and in combination. However, the combination of durvalumab tremelimumab and palliative radiation has not been previously studied, this study will include a formal safety analysis in the first 6 patients accrued. Enrollment will be halted until these first 6 patients complete the first two cycles of treatment (8 weeks), and are evaluable for acute toxicities (toxicities reported within the 1st 8 weeks after treatment initiation). Specifically, if 2 or more DLTs (Refer to Section 6.4) are observed, then, durvalumab dosing will be modified to 1500 mg IV Q6 weeks x 9 doses and tremelimumab 75mg IV Q6 weeks x 3 doses for the remaining 14 patients (fixed dosing for patients > 30kg). If 1 or fewer DLTs are observed, then an additional 14 patients will be enrolled and treated at the initial dose and schedule of durvalumab and tremelimumab. Patients in the run in phase who experience DLTs will undergo dose modifications described in Appendix 1.

Toxicities will be graded based on CTCAE v. 4 and summarized as the number and percentage of patients with each type of toxicity. Responses will be summarized as frequencies and percentages. The Kaplan Meier method will be used to estimate overall survival and progression free survival. Outcomes will be calculated from the date of study entry to the date of the corresponding event.

We will use multivariate statistics to test the hypotheses that pretreatment intratumoral immune cell phenotype and PD-L1 expression predict response to therapy, and that therapy alters systemic immunophenotype.

Sample Size Determination:

There are multiple ongoing studies in various tumor types exploring the activity of durvalumab and tremelimumab. In a published report of the combination in patients with advanced NSCLC treated on a phase Ib study, Grade 3-4 toxicity was observed in 17% of patients. Similarly, in single institution reports of SBRT with the monoclonal antibody, grade 3 or higher toxicity was reported in 6-16% of patients. With a 20 patient accrual goal, toxicity rates can be estimated to within 22% with 95% confidence. Any toxicity with at least 10% prevalence has at least an 87% chance of being observed. This design allows us to reasonably exclude a clinically significant increase in toxicity with the addition of radiation therapy to the durvalumab and tremelimumab combination as defined by the upper bound of the confidence interval.

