The response rates to dual CTLA and PDL1 blockade and radiation therapy after prior immunotherapy are unknown. If objective responses are demonstrated, or encouraging progression free survival is observed in the 20 patients enrolled on the study, it would merit further investigation in a larger study powered to examine efficacy endpoints.

SCHEDULE OF STUDY ASSESSMENTS

Assessments to be performed at the times stipulated in the table and as clinically required in the management of the subject	Screening	all assessments to be performed pre-infusion unless stated otherwise				
		cycle 1		cycle 2 - 4	cycle 5 -13	
		week 1	week 3	week 1	week 1	end of treatment
Day	- 28 to - 1	Day 1 of the Week				
Week	-4 to -1	(±3 days)			(±7 days)	
Written informed consent	X					
Demography and history of tobacco and alcohol use	X					
Previous treatments for head and neck cancer	X					
Tumor tissue sample (Section 8.3.2)	X					
Formal verification of eligibility criteria	X					
Medical and surgical history	X					

Assessments to be performed at the times stipulated in the table and as clinically required in the management of the subject	Screening	all assessments to be performed pre-infusion unless stated otherwise					
		cycle 1		cycle 2 - 4		cycle 5 - 13	
		week 1	week 3	week 1	week 1	end of treatment	LTFM
Day	- 28 to - 1	Day 1 of the Week					
Week	-4 to -1	(±3 days)		(±7 days)			
Urine hCG or serum βhCG ^b	X						
Physical examination ^c	X	X	X	X	X	X	
Vital signs	X	X	X	X	X	X	
Weight	X	X		X	X		
Electrocardiogram ^d	X						
Durvalumab administration ^e		X		X	X		
Tremelimumab administration ^e		X		X		X	
Adverse event/serious adverse event assessment	X	All Visits					
Radiation therapy evaluation and radiation planning/simulation	X						
Palliative Radiation therapy		XRT to begin 2 weeks after the first dose of Durvalumab and tremelimumab and to be completed in 2 weeks					
ECOG performance status	X	X	X	x	X	X	

Assessments to be performed at the times stipulated in the table and as clinically required in the management of the subject	Screening	all assessments to be performed pre-infusion unless stated otherwise					
		cycle 1		cycle 2 - 4		cycle 5 - 13	
		week 1	week 3	week 1	week 1	end of treatment	LTfM
Day	- 28 to - 1	Day 1 of the Week					
Week	-4 to -1	(±3 days)			(±7 days)		
TSH with reflexive free T4 ^f		X		X ^f	X ^f		
Complete blood count ^g	X	X	X	X	X	X	
Serum chemistry ^g	X	X	X	X	X	X	
Urinalysis ^h	X		X				
Coagulation parameters ⁱ	X	as clinically indicated					

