3.2 Study Schema

The first 6 patients of this study will represent the initial run-in phase of the triplet combination of durvalumab, tremelimumab and HIGRTor SBRT. Fixed doses of Durvalumab and Tremelimumab will be administered on day 1 of therapy. Radiation will be initiated on Week 3 of the 28 day cycle. Radiation will be delivered to a total dose of 24 Gy, given in 3 fractions of 8Gy every other day. Durvalumab will be continued for a total of 13 cycles, and tremelimumab for a total of 4 cycles unless patient withdraws consent, has confirmed disease progression, and/or develops toxicity that results in treatment discontinuation.

Serum correlative studies will be collected at the following timepoints: at baseline, prior to cycle #2, and prior to cycle#4 of treatment. Archived formalin fixed paraffin embedded tissue will be collected from patients enrolled. If the patient does not have archived tissue available, a fresh biopsy will be obtained.

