3.3 Study Oversight for Safety Evaluation

The primary endpoint of this study is safety and tolerability. Durvalumab and tremelimumab will be given at the recommended fixed dosing in patients > 30kg (see section 1.3.1), which has been shown to result in minimal toxicity, but encouraging efficacy in NSCLC patients. Since the concurrent administration of radiation therapy is previously unstudied in this cohort, the first 6 patients will represent a run-in phase, and enrollment will be halted until all patients complete

the first two cycles of treatment (8weeks) These 6 patients will be assessed for DLTs and will determine if a modified dosing schedule of durvalumab and tremelimumab will be applied in the expansion phase.

In keeping with the study primary endpoint, a stopping rule will be implemented in the unlikely event that the combination under study is deemed to have unacceptably high toxicities. Enrollment will be halted if more than 3 patients experience a Grade 4 or higher drug related toxicity (CTCAE v. 4) during the trial or up to 30 days after the last investigational drug infusion. The likelihood of observing 3 or more Grade 4+ drug-related DLTs is 80% if the true rate is 20% and the likelihood is 91% if the true rate is 25%. This rule has an 83% chance of stopping in the 1st 10 patients if the true rate is 40%. Section 10.2.2 provides some guidelines on the attribution of toxicity to the drug and radiation combination. The study will be reviewed by the University of Washington/Fred Hutchinson Cancer Research Center Data Safety and monitoring board.

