5.3.3. Radiation Treatment planning, dose fractionation and organs at risk specification

Computer based planning & quality assurance (QA) will be performed using our standard institutional HIGRT and SBRT guidelines, to deliver HIGRT or SBRT to the index lesion(s), including static 3D coplanar and/or non-coplanar beam arrangements as well as dynamic conformal arcs. Corrections for tissue heterogeneity, and robustness analysis (for Proton therapy) will be made. Treatment planning may be performed with 3D-CRT, IMRT, VMAT or, Proton beam RT (Pencil beam RT or Uniform scanning).

3D coplanar or non-coplanar beam arrangements will be custom designed for each case to deliver highly conformal prescription dose distributions. Non-opposing, non-coplanar beams are preferable. Typically, $>/= 5-10$ beams of radiation will be used with roughly equal weighting. Generally, more beams are used for lesions that are in very close proximity to a critical OAR to produce appropriately protective concave dose distributions with a steep dose gradient between the target lesion and the OAR.

For arc rotation techniques, a minimum of 340 degrees (cumulative for all beams) should be utilized.

Proton beam planning is performed with 2-4 beams. In order to obtain acceptable coverage, field aperture size and shape should correspond nearly identically to the projection of the PTV along a beam's eye view (i.e., no additional "margin" for dose buildup at the edges of the blocks or MLC jaws beyond the PTV). The only exception should be when observing the minimum field dimension of 3.5 cm when treating small lesions (see above).

Radiotherapy prescription: The dose prescription will be as follows: 24 Gy given in 3 fractions to PTV (80-95% IDL) delivered at 8 Gy per fraction every other day. however, a dose reduction to 6 Gy per fraction will be permitted if 8 Gy is not achievable due to dose constraints.

Dose Uniformity: 95% of the planning target volume (PTV) should be covered by the prescription dose (PTV V95%RX = 100%) and 99% of the planning target volume (PTV) should receive a minimum of 90% of the prescription dose (PTV V99%RX > 90%). 99% of the CTV should receive a minimum of 98% of the prescribed dose (CTV V99%RX >98%); however, higher isodoses (hotspots) of $> 105\%$ of prescribed dose must be manipulated to occur within the target and not in adjacent normal tissue.

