6.4 Definition of DLT

Dose-limiting toxicities (DLTs) will be evaluated during the run in phase consisting of the first 6 patients enrolled in this trial. The period for evaluating DLTs will be from the time of first administration of durvalumab or tremelimumab until 28 days (cycle 1). Adverse event monitoring will continue for these subjects throughout the course of their treatment (beyond cycle 1) as outlined in the Schedule of Study Assessments, these adverse events will include potential XRT related toxicities. Subjects who do not remain on the study up to this time for reasons other than DLT will be replaced with another subject. Grading of DLTs will follow the guidelines provided in the Common Terminology Criteria for Adverse Events (CTCAE) version 4.0.

A DLT will be defined as any Grade 3 or higher toxicity that occurs during the DLT evaluation period. Toxicity that is clearly and directly related to the primary disease or to another etiology is excluded from this definition. The following will be DLTs:

- Any Grade 4 irAE
- Any \geq Grade 3 colitis
- Any Grade 3 or 4 noninfectious pneumonitis irrespective of duration
- Any Grade 2 pneumonitis that does not resolve to \leq Grade 1 within 3 days of the initiation of maximal supportive care
- Any Grade 3 irAE, excluding colitis or pneumonitis, that does not downgrade to Grade 2 within 3 days after onset of the event despite optimal medical management including systemic corticosteroids or does not downgrade to \leq Grade 1 or baseline within 14 days
- Liver transaminase elevation $> 8 \times$ ULN or total bilirubin $> 5 \times$ ULN
- Any \geq Grade 3 non-irAE, except for the exclusions listed below
 - Grade 3 fatigue lasting \leq 7 days
 - Grade 3 endocrine disorder (thyroid, pituitary, and/or adrenal insufficiency) that is managed with or without systemic corticosteroid therapy and/or hormone replacement therapy and the subject is asymptomatic
 - Grade 3 inflammatory reaction attributed to a local antitumor response (eg, inflammatory reaction at sites of metastatic disease, lymph nodes, etc)
 - Concurrent vitiligo or alopecia of any AE grade
 - Grade 3 infusion-related reaction (first occurrence and in the absence of steroid prophylaxis) that resolves within 6 hours with appropriate clinical management

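### No run-in counting rule sets a minimum radiation exposure, so a patient who receives little or no radiation can count as a DLT-free triplet patient

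*Combined protocol and SAP*

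**What the plan says.** Section 3.2 describes the purpose of the run-in: "The first 6 patients of this study will represent the initial run-in phase of the triplet combination of durvalumab, tremelimumab and HIGRTor SBRT". Section 3.3 gives the reason: "Since the concurrent administration of radiation therapy is previously unstudied in this cohort, the first 6 patients will represent a run-in phase".

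Three pieces of text bear on who counts among the six:

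- Section 4.4 leaves out of the DLT rate, and replaces, a patient without a DLT who falls under an exposure limit: "Patients who received <90% of the durvalumab and tremelimumab infusion in Cycle 1".
- Section 6.4 sets a 28-day DLT period starting at the first drug dose and adds a retention rule: "Subjects who do not remain on the study up to this time for reasons other than DLT will be replaced with another subject".
- The synopsis sets a hold, repeated in shorter form in 3.3: "Enrollment will be halted until these first 6 patients complete the first two cycles of treatment (8 weeks), and are evaluable for acute toxicities".

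On radiation, the Schedule of Study Assessments says "XRT to begin 2 weeks after the first dose of Durvalumab and tremelimumab and to be completed in 2 weeks". The synopsis and 3.2 describe 24 Gy in 3 fractions. Section 5.3.3 adds: "however, a dose reduction to 6 Gy per fraction will be permitted if 8 Gy is not achievable due to dose constraints".

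The decision rule is in the synopsis and Section 6.2. With 0 or 1 DLT, 14 more patients are treated on the initial drug schedule. With 2 or more, those 14 receive both drugs every 6 weeks instead of every 4.

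**The concern.** The plan guards against under-exposure to the two drugs, whose combined toxicity it calls well established, but not against under-exposure to the component it calls unstudied. The infusion rule is met or failed at the first dose, two weeks before radiation begins. The retention rule asks only whether the patient is still on study at Day 28.

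Consider a patient who receives both infusions in full and attends to Day 28, but whose radiation is cancelled, postponed beyond the window or stopped after one fraction. Applied as written, 4.4 and 6.4 count that patient as one of the six without a DLT, and nothing triggers replacement. Such a patient carries roughly the DLT risk of the drugs alone. If radiation adds risk, which is the question the run-in asks, the count is pulled down and the rule is more likely to keep the initial drug schedule for the expansion.

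**Working it through.** **1. The counting text, side by side**

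| Text | What it tests | Radiation term |
|---|---|---|
| 4.4 | At least 90% of the cycle 1 infusion | None |
| 6.4 | On study to Day 28, unless a DLT occurred | None |
| Synopsis and 3.3 hold | Two cycles (8 weeks) completed; the synopsis adds evaluable for acute toxicity | Not stated; neither treatment nor evaluable is defined |
| 11.1 and 11.2.1 | All enrolled, including replaced patients | None |

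No analysis set restores an irradiated denominator for the run-in decision.

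**2. The plan's own figures.** Section 11.3 gives a precision of 22% and an 87% chance of seeing a toxicity of 10% prevalence, both for 20 patients. These reproduce: 1.96 × √(0.25/20) = 0.219, and 1 − 0.9^20 = 0.878. They are not affected by this point. The plan states no operating characteristic for the 2-of-6 rule.

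**3. Effect on the 2-of-6 rule.** Let m of the six be irradiated with DLT probability pT, and k = 6 − m not irradiated with probability pD, all independent. Then

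P(0 or 1 DLT) = (1−pT)^m (1−pD)^k + m pT (1−pT)^(m−1) (1−pD)^k + (1−pT)^m k pD (1−pD)^(k−1),

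and P(2 or more) is one minus this.

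Inputs: pD = 17% is the Grade 3-4 toxicity figure for the drug combination in 11.3, used as a proxy. It is not a DLT rate, so 10% is shown as well. The values of pT and m are assumptions.

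With pT = 0.40 and pD = 0.17:

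- m = 6: 1 − (0.0467 + 0.1866) = 0.767
- m = 5: 1 − (0.0778×0.83 + 0.2592×0.83 + 0.0778×0.17) = 1 − 0.293 = 0.707
- m = 4: 1 − (0.1296×0.6889 + 0.3456×0.6889 + 0.1296×0.2822) = 1 − 0.364 = 0.636

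P(2 or more DLTs of 6) over a range of assumptions:

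| pT | pD | m = 6 | m = 5 | m = 4 |
|---|---|---|---|---|
| 25% | 17% | 0.466 | 0.434 | 0.402 |
| 33% | 17% | 0.642 | 0.589 | 0.531 |
| 40% | 17% | 0.767 | 0.707 | 0.636 |
| 50% | 17% | 0.891 | 0.839 | 0.767 |
| 25% | 10% | 0.466 | 0.407 | 0.345 |
| 40% | 10% | 0.767 | 0.689 | 0.592 |

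If pT equals pD, the number irradiated makes no difference.

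**4. Information on the triplet.** With no DLTs, the one-sided 95% upper bound on the triplet DLT rate is 1 − 0.05^(1/m): 39% for six irradiated patients, 45% for five and 53% for four.

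**The case against.** The strongest reply is that the gap will seldom open. Eligibility requires a lesion judged suitable for radiation and the ability to tolerate the procedures (4.1, items 6 and 7). Planning and simulation take place at screening, and the course is three fractions at one centre. Section 4.3 allows withdrawal for noncompliance, and withdrawal before Day 28 would trigger replacement under 6.4. The synopsis lists radiation among the treatments that every patient receives, so completing two cycles of treatment can naturally be read to include it. All of this stands as a reason to expect few missed courses. It does not supply a counting rule: 4.3 permits withdrawal without requiring it, and the hold leaves its terms undefined.

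The size is also open to challenge. The 17% proxy could err either way: 6.4 excludes several Grade 3 events from the DLT definition, and 1.3.1 reports no DLTs in the 11-patient cohort at the corresponding weight-based doses. The only figure in 11.3 for SBRT with an antibody is 6-16% Grade 3 or higher, well below the triplet rates assumed here. With one missed course and a 25% triplet rate the loss is about 3 percentage points. This stands, and the probabilities are illustrative.

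Three stronger readings are tempting, and the documents do not support them.

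- A reader might infer that evaluability rests on the drug infusion alone. It does not: 6.4 adds retention, and the synopsis and 3.3 add the hold.
- A reader might infer that a patient given 6 Gy per fraction (3 × 6 = 18 Gy if three fractions are kept) did not receive the triplet. Section 5.3.3 expressly permits that reduction, so such a patient had protocol treatment.
- A reader might infer that the run-in decides whether the triplet continues. Fourteen more patients follow either way, and only the drug schedule changes. The Grade 4 or higher stopping rule in 3.3, the monitoring board's review and the all-enrolled toxicity analysis all remain.

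**Conclusion.** The point holds. The run-in is there to test the addition of radiation, and the stated counting rules, followed exactly, admit a patient who had little or none as a DLT-free member of the six. The direction of the bias is towards keeping the initial drug schedule, provided that radiation raises DLT risk.

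The size cannot be fixed from the documents. At an assumed 40% triplet rate with the 17% proxy, one unirradiated patient costs about 6 percentage points of the chance of 2 or more DLTs (77% to 71%), and two cost about 13 (77% to 64%). At a 25% triplet rate the losses are about 3 and 6 points.

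This should be fixed, but it is not critical. Safeguards against missed radiation exist, the consequence is confined to the drug schedule for 14 patients, and trial-wide safety monitoring continues. The documents do not show that any run-in patient will go unirradiated.

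**What to change.** In 4.4 and 6.4, state that a run-in patient without a DLT is evaluable only if, besides meeting the existing infusion rule, the patient received a sponsor-specified minimum of the planned radiation and was followed to the end of the DLT window. Replace those who fall short, and keep them in the all-enrolled toxicity analysis of 11.1. A DLT counts whenever it occurs in the window, including before radiation. The count is then not purely a triplet count, but this is the same convention that 4.4 already applies to incomplete infusions, and it errs on the cautious side.

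Report the radiation delivered to each run-in patient. A separate analysis by radiation dose in six patients would not be informative and is not needed.

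Reconcile the following at the same time:

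- the 28-day DLT period in 6.4 with the 8-week assessment in the synopsis and 3.3, and state whether completing the two cycles includes radiation;
- the closing line of 4.2, which rules out replacing withdrawn patients, with the replacement rules in 4.4 and 6.4;
- replacement with the maximum of 20 patients and the expansion of 14;
- the 24 Gy description in the synopsis and 3.2 with the reduction allowed in 5.3.3.

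The cost is a sentence in each of 4.4 and 6.4 plus these reconciliations, possibly one replacement patient, and a short delay before expansion. No new procedure is needed.

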5. INVESTIGATIONAL PRODUCT(S)

5.1 Durvalumab and tremelimumab

The Investigational Products Supply section of AstraZeneca/MedImmune will supply durvalumab and tremelimumab to the investigator as solutions for infusion after dilution.

5.1.1 Formulation/packaging/storage

Durvalumab

Durvalumab will be supplied by AstraZeneca as a 500-mg vial solution for infusion after dilution. The solution contains 50 mg/mL durvalumab, 26 mM histidine/histidine-hydrochloride, 275 mM trehalose dihydrate, and 0.02% (weight/volume) polysorbate 80; it has a pH of 6.0. The nominal fill volume is 10.0 mL. Investigational product vials are stored at 2°C to 8°C (36°F to 46°F) and must not be frozen. Durvalumab must be used within the individually assigned expiry date on the label.

Tremelimumab

Tremelimumab will be supplied by AstraZeneca as a 400-mg or 25-mg vial solution for infusion after dilution. The solution contains 20 mg/mL of tremelimumab, 20 mM histidine/histidine hydrochloride, 222 mM trehalose dihydrate, 0.02% (w/v) polysorbate 80, and 0.27 mM disodium edetate dihydrate (EDTA); it has a pH of 5.5. The nominal fill volume is 20.0 mL. Investigational product vials are stored at 2°C to 8°C (36°F to 46°F) and must not be frozen. Tremelimumab must be used within the individually assigned expiry date on the label.

5.2 Dose and treatment regimens

5.2.1 Treatment regimens

Durvalumab + tremelimumab combination therapy

Patients (> 30kg in weight) will receive 1500 mg durvalumab via IV infusion q4w for up to 4 doses/cycles and 75 mg tremelimumab via IV infusion q4w for up to 4 doses/cycles, and then continue 1500 mg durvalumab q4w starting on Week 16 for a total of 13 doses. Dosing outside the window should be discussed with the Study Physician. Tremelimumab will be administered first. Durvalumab infusion will start 1 hour (+/- 5 mins.) after the end of tremelimumab infusion. The duration will be 1 hour(+/- 5 mins.) for each infusion. A 1 hour (+/- 5 mins.) observation period is required after the first infusion of durvalumab and tremelimumab. If no clinically significant infusion reactions are observed during or after the first cycle, subsequent infusion observation periods can be at the Investigator's discretion (suggested a minimum of 30 minutes after each durvalumab and tremelimumab infusion).

